6.0 Study Treatment Duration and Compliance

Duration of treatment will be summarized for each treatment group on SS1 for Period 1, SS2 for Period 2 and SS LT across Period 1 and Period 2.

Duration of treatment will be summarized using the number of subjects treated, mean, standard deviation, median, minimum and maximum.

Study Drug Duration (in Days) in Period 1:

• Date of last dose of study drug in Period 1 Date of first dose of study drug in Period 1 + 1

Study Drug Duration (in Days) in Period 2:

• Date of last dose of study drug in Period 2 Date of first dose of study drug in Period 2 + 1

Study Drug Duration (in Days) for SS LT:

• Date of last dose of study drug - Date of first dose of study drug + 1

In addition, the number and percentage of subjects exposed to study drug will be summarized for the following cumulative duration intervals for SS1 and SS LT.

- $\geq 1 \text{ day}$
- ≥ 2 weeks
- \bullet > 4 weeks
- ≥ 12 weeks
- \geq 24 weeks

- \bullet > 36 weeks
- \geq 48 weeks
- \geq 60 weeks
- \geq 72 weeks
- \geq 84 weeks
- > 96 weeks

Treatment compliance will be summarized for each treatment group on SS1 for Period 1, SS2 for Period 2, and SS LT across Period 1 and Period 2. Treatment compliance is defined as the number of tablets actually taken divided by the number of tablets that should have been taken. Percent compliance will be summarized.

7.0 Subject Characteristics

Categorical variables will be summarized with the number and percentage of subjects. Continuous variables will be summarized with descriptive statistics (number of non-missing observations, mean and standard deviation, median, minimum and maximum).

7.1 Demographics and Baseline Characteristics

Demographics and selected Baseline characteristics will be summarized descriptively, overall and by treatment group (or treatment sequence) for FAS1 and FAS2. Unless otherwise specified, "Baseline" is defined as the last non-missing value on or before the day of the first administration of study drug or randomization if no study drug is given.

Categorical demographic variables include:

- Sex (Male, Female)
- Race (White, Black or African American, Asian, American Indian or Alaska Native, Native Hawaiian or Other Pacific Islander, Multiple)
- Race Group (White, Non-White)
- Ethnicity (Hispanic or Latino, Not Hispanic or Latino)
- Age Group 1 (< 65 years, \ge 65 years)

[figure not shown]
- Age Group 2 (< 65 years, \ge 65 and < 75 years, \ge 75 years)
- Body Mass Index (BMI) Group ($< 25 \text{ kg/m}^2$, $\ge 25 \text{ kg/m}^2$ and $< 30 \text{ kg/m}^2$, $\ge 30 \text{ kg/m}^2$)
- Geographic Region Group (North America, Western Europe, Eastern Europe, Asia, Oceania)
- Nicotine User (Current, Former, Never, Unknown)
- Alcohol User (Current, Former, Never, Unknown)

Continuous demographic variables include:

- Age (years)
- Weight (kg)
- Height (cm)
- BMI (kg/m²)

Selected Baseline characteristics include:

- Prior Use of IL-6 Inhibitor (Yes, No)
- New Onset of GCA (Yes, No)
- Baseline CS Dose (mg)
- Baseline CS Dose Group ($> 30 \text{ mg}, \le 30 \text{ mg}$)
- Disease Duration since Diagnosis (years)
- Baseline C-Reactive Protein (mg/dL)
- Baseline Erythrocyte Sedimentation Rate (mm/hr)
- Ischemia-Related Vision Loss (Yes, No)
- History of Unequivocal Symptoms of PMR Symptom without Cranial Symptoms of GCA (Yes, No)
- Baseline FACIT-Fatigue Score
- Baseline SF-36 Score (PCS, Mental Component Summary (MCS), the 8-Sub-domain Scores)
- Baseline EQ-5D-5L

• Baseline PGA

[figure not shown]
7.2 Medical History and Prior and Concomitant Medications

Medical history data will be coded using the Medical Dictionary for Regulatory Activities (MedDRA). The actual version of the MedDRA coding dictionary will be noted in the statistical tables and clinical study report. The number and percentage of subjects in each medical history category (by MedDRA system organ class (SOC) and preferred term) will be summarized overall and by treatment group for FAS1. The SOC will be presented in alphabetical order, and the preferred terms will be presented in alphabetical order within each SOC. Subjects reporting more than one condition/diagnosis will be counted only once in each row (SOC or preferred term).

Prior medication will be summarized for FAS1. Concomitant medications will be summarized separately for FAS1 and FAS2. A prior medication is defined as any medication taken prior to the date of the first dose of study drug. A concomitant medication is defined as any medication that started prior to the date of the first dose of study drug and continued to be taken after the first dose of study drug or any medication that started on or after the date of the first dose of study drug, but not after the date of the last dose of study drug + 1 day. The number and percentage of subjects taking prior and concomitant medications will be summarized by generic drug name, based on the World Health Organization (WHO) Drug Dictionary. The actual version of the WHO Drug Dictionary will be noted in the statistical tables and clinical study report.

7.3 Protocol Deviations

Protocol deviations include eligibility criteria violations, receipt of wrong treatment or incorrect dose of study treatment, development of withdrawal criteria without being withdrawn, and use of prohibited concomitant medications.

For each of the following protocol deviation categories and across all categories, the number and percentage of randomized subjects with at least one protocol deviation will be summarized overall and by treatment group:

- Subject entered into the study even though did not satisfy entry criteria;
- Subject developed withdrawal criteria during the study but was not withdrawn;
- Subject received wrong treatment or incorrect dose of study treatment;
- Subject took prohibited concomitant medication.

8.0 Handling of Potential Intercurrent Events for the Primary and Multiplicity-Controlled Secondary Endpoints

The primary endpoint and multiplicity-controlled secondary endpoints (defined in Section 3.1 and Section 3.2) will be analyzed based on FAS1, except for the endpoint of the rate of CS-related AEs which will be analyzed based on SS1.

[figure not shown]
Intercurrent Events (ICEs):

- ICE1: Premature discontinuation from study treatment
- ICE2: Investigator-initiated CS escape therapy
- ICE3: Received more than 100 mg prednisone (or equivalent) systemic CS for a non-GCA indication

The following method will be used to address potential intercurrent events above:

For the primary analysis of the primary efficacy endpoint, estimand with composite and hypothetical strategy will be used. For ICE1: subjects will be considered as non-responders after ICE1. ICE2 is not applicable for the primary endpoint. For ICE3: data after ICE3 will be handled by multiple imputation (MI).

For the primary analysis of the multiplicity-controlled secondary binary remission related efficacy endpoints, estimands with composite and hypothetical strategy will be used. For

ICE1: subjects will be considered as non-responders after ICE1. ICE2 is not applicable for remission related endpoints. For ICE3: data after ICE3 will be handled by MI.

For the primary analysis of the secondary binary efficacy endpoint of proportion of subjects who experience at least 1 disease flare through Week 52, estimand with treatment policy strategy to handle ICEs will be used: data collected will be used regardless of ICE1 or ICE3. ICE2 is not applicable for the endpoint of proportion of subjects who experience at least 1 disease flare.

[figure not shown]
For the primary analysis of the secondary continuous efficacy endpoints (except for cumulative CS exposure), estimands with treatment policy and hypothetical strategy to handle ICEs will be used: data collected will be used regardless of ICE1 or ICE3. Data collected after ICE2 will be excluded and missing data will be handled by mixed effect model repeat measurement (MMRM).

For the primary analysis of secondary endpoint of cumulative CS exposure, estimand with treatment policy strategy to handle ICEs will be used: data collected will be used regardless of ICE1, ICE2, or ICE3.

For the primary analysis of secondary time-to-event endpoint (i.e., time-to-first disease flare), estimand with treatment policy strategy to handle ICEs will be used: data will be used regardless of ICE1 or ICE3. ICE2 is not applicable for the endpoint of time-to-first disease flare.

For the primary analysis of secondary count endpoint (i.e., number of disease flares per subject), estimand with treatment policy strategy to handle ICEs will be used: data will be used regardless of ICE1 or ICE3. ICE2 is not applicable for the endpoint of number of disease flares per subject.

For the primary analysis of the secondary efficacy endpoint of rate of CS-related AEs, estimand with treatment policy strategy to handle ICEs will be used: data collected will be used regardless of ICE1, ICE2, or ICE3.

9.0 Efficacy Analyses

9.1 General Considerations

All efficacy analyses will be conducted on the FAS in each period. All Period 1 efficacy analyses will be conducted using FAS1. All Period 2 efficacy analyses will be conducted using FAS2. In addition, per-protocol analysis for the primary endpoint will be performed in the Per-Protocol Analysis Set.

The Primary Analysis will be performed after all subjects have completed Period 1 and the database has been locked. This will be the final analysis for all primary and multiplicity-controlled secondary endpoints as well as all additional efficacy endpoints in Period 1.

The primary and multiplicity-controlled secondary endpoints as specified in Section 3.0 will be tested with graphical multiplicity adjustment 1,2 to ensure a strong control of family-wise type I error rate at 2-sided $\alpha = 0.05$.

[figure not shown]
The final analysis will be performed after all subjects have either withdrawn from the study or completed Period 2 and safety follow-up.

For analyses with stratification factors used for randomization, any subject who is randomized within an incorrect stratum will be analyzed according to the actual stratum to which the subject belongs, unless otherwise indicated. The stratification factor of prior use of an IL-6 inhibitor (yes, no) will be removed from the models for all analyses due to the small number (17 [approximately 4.0%] out of 428 total) of prior IL-6 inhibitor users enrolled.

9.2 Handling of Missing Data

Non-Responder Imputation incorporating multiple imputation (NRI-MI)

The NRI-MI will be the primary approach to handle missing data for binary primary and secondary endpoints (except for the endpoints of proportion of subjects who experience at

[figure not shown]
least 1 disease flare). The NRI-MI will categorize any subject who does not have an evaluation during a pre-specified visit window (either due to missing assessment, early withdrawal from the study, or due to intercurrent event) as a non-responder for the visit. The only exceptions are: 1) when a subject is a responder both before and after the visit window, the subject will be categorized as a responder for the visit. 2) missing data due to COVID-19 logistical restriction will be handled by MI. The MI assumes data are missing at random (MAR). In total, 30 datasets will be imputed, and results from the 30 datasets will be synthesized following Rubin's formula. All assessments after an intercurrent event occurs will be handled as specified in Section 8.0. For example, for the primary endpoint, all assessments after the visit date of ICE1 will not be included in the analyses; as a result, subjects will be counted as non-responders thereafter and will not be imputed by MI.

As Observed (AO)

The AO analysis will not impute values for missing evaluations, and thus a subject who does not have an evaluation on a scheduled visit will be excluded from the AO analysis for that visit. All observed data will be used in the analysis. AO analysis will be the primary approach to analyze disease flare endpoints (including proportion of subjects who experience at least 1 disease flare through Week 52, time to first disease flare through Week 52, and number of disease flares per subject through Week 52), cumulative CS exposure, and rate of CS-related AEs.

Mixed Effect Model Repeat Measurement (MMRM)

MMRM will be the primary approach for the analysis of continuous variables with more than one post Baseline assessment, except for the endpoint of cumulative CS exposure. MMRM analysis will be conducted using mixed model including observed measurements at all visits. The mixed model includes the categorical fixed effects of treatment, visit and treatment-by-visit interaction, stratification factors at randomization (Baseline CS dose [prednisone or prednisolone \geq 30 mg, prednisone or prednisolone \leq 30 mg], and Baseline disease status [new onset disease, relapsing disease]), and the continuous fixed covariates

of Baseline measurement (when applicable). An unstructured variance covariance matrix will be used. If the model cannot converge, an appropriate alternative covariance structure (e.g., autoregressive (1) or compound symmetry) will be used. The parameter estimations will be based on the assumption of data being missing at random and the method of restrictive maximum likelihood (REML) will be used.

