For continuous change from baseline endpoints such as change from baseline in SF-36, PGA, EQ-5D-5L and FACIT-Fatigue, comparisons between the upadacitinib treatment groups and the PBO group will be carried out using the Mixed-Effect Model Repeat Measurement (MMRM) model with treatment group, visit, treatment-by-visit interaction, and stratification factors as the fixed factors and the corresponding baseline values as the covariates. TSQM, PGIC value will be analyzed using an MMRM model with treatment group, visit, treatment-by-visit interaction and stratification factors as the fixed factors. For cumulative CS dose, comparisons between the upadacitinib treatment group and the PBO group will be analyzed using a van Elteren test stratified by stratification factors. The median total cumulative prednisone dose over the 52 weeks for each treatment group and the corresponding 95% CI for the median will be presented.

For time-to-event endpoints, median time-to-event will be reported for each treatment group. Comparisons between the upadacitinib group and the PBO group will be conducted using stratified log

rank test; additional analyses may be conducted using Cox's regression to include baseline values and stratification factors as covariates.

For count endpoints, comparisons between the upadacitinib treatment group and the PBO group will be carried out using Poisson regression model with treatment group and stratification factors as covariates, adjusting for exposure duration.

Other Efficacy Variables

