For the time to event endpoint (i.e., time to first disease flare), median time-to-event will be reported for each treatment group. Treatment comparisons in the distribution of time-to-event between each upadacitinib group and the placebo will be conducted using stratified log-rank test stratified by stratification factors. Median time for each treatment group will be provided based on Kaplan-Meier estimate. Subjects who never achieve the three criteria required before disease flare is considered (Section 9.4.1) during the treatment period will be censored at Baseline. Subjects who achieve the three criteria required before disease flare but never experience disease flare will be censored at the last assessment in Period 1. Analyses using Cox proportional hazards model with stratification factors as covariates will also be performed. Corresponding p-values, hazard ratios and 95% CIs will be reported.

For count endpoints (i.e., number of disease flare per subject and CS-related AEs), comparisons between each upadacitinib treatment group and the placebo group will be carried out using Poisson regression model with stratification factors as covariates, adjusted by the duration of study participation (or duration of study drug exposure for CS-related AEs). Log-transformation and robust standard error will be used in the Poisson regression model.

[figure not shown]
For all secondary binary endpoints (except for sustained complete remission and proportion of subjects who experience at least 1 disease flare), summary statistics will be provided for each treatment group using AO data. For all secondary continuous endpoints (except for cumulative CS exposure), an ANCOVA model will be applied based on AO data, with categorical fixed effects of treatment, stratification factors at randomization (Baseline CS dose [prednisone or prednisolone > 30 mg, prednisone or prednisolone ≤ 30 mg], and Baseline disease status [new onset disease, relapsing disease]), and the continuous fixed covariates of Baseline measurement (where applicable) in the model.

[figure not shown]
The attributes of the estimands corresponding to the multiplicity-controlled secondary efficacy objectives are summarized in Table 2.

Table 2. Summary of the Estimand Attributes Corresponding to the Multiplicity-Controlled Secondary Efficacy Endpoints

	Attributes of the Estimand					
Estimand Label	Treatment	Endpoint	Handling of Population Intercurrent Events		Statistical Summary	

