To assess the impact of potential departures from the missing at random assumption, tipping point analyses are conducted as a sensitivity check for change from Baseline in the multiplicity-controlled secondary continuous endpoints at Week 52.

The tipping point analyses are two-dimensional, i.e., assumptions about the missing outcomes on the upadacitinib treatment groups and the placebo group can vary independently. In addition, the focus is on scenarios where missing outcomes on upadacitinib are worse than the imputed values on upadacitinib, while missing outcomes on placebo are better than the imputed values on placebo, for the visit of interest. Missing values are first imputed via MI under MAR assumption using data before ICEs at all visits, and then a shift parameter is applied to the imputed values of the visit of interest (a different shift parameter may be specified for each treatment group). This is implemented by PROC MI using the MNAR statement. The number of imputed datasets is 30.

More specifically, PROC MI using the sequential fully conditional specification (FCS) method⁵ will be performed to impute any missing value and does not rely on a monotone missing pattern. It also can achieve the exact shifted values for tipping point analysis. Treatment is included in the FCS imputation model to enable sampling conditional on treatment groups. Additionally, the imputation model includes the same stratification factors that are used in the primary analysis and the Baseline value of the endpoints of interest, as well as longitudinal response observed at any other prior visits.

For a given pair of shift parameters, the SAS code example is as follows. Prior to the code below, any missing Baseline categorical variables are singly imputed with the most common level of each variable. Any missing baseline continuous variables are handled with FCS based on other baseline variables. Assessment at Baseline was not collected for TSQM. Thus, consideration for Baseline in the model is not applicable for TSQM.

```
PROC MI DATA=DATA WIDE OUT=DATA WIDE BOUNDED NIMPUTE=30
SEED=12345;
   CLASS TRTP &COVCAT;
   VAR trtp &COVCON &COVCAT WEEK 8 WEEK 12 WEEK 24 WEEK 52;
   /* FCS for baseline continuous variables */
   FCS reg(base = trtp &COVCAT);
   /* Sequential FCS for endpoint at different visits */
   FCS reg(WEEK 8 = trtp &COVCAT &COVCON);
   FCS reg(WEEK 12 = trtp &COVCAT &COVCON WEEK 8);
   FCS reg(WEEK 24 = trtp &COVCAT &COVCON WEEK 8 WEEK 12);

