   FCS reg(WEEK 52 = trtp &COVCAT &COVCON WEEK 8 WEEK 12
   WEEK 24);
  MNAR ADJUST (WEEK 52 / SHIFT=&SJ1
   ADJUSTOBS=(TRTP='PLACEBO'));
  MNAR ADJUST (WEEK 52 / SHIFT=&SJ2 ADJUSTOBS=(TRTP='UPA
   7.5MG'));
  MNAR ADJUST (WEEK 52 / SHIFT=&SJ2 ADJUSTOBS=(TRTP='UPA
   15MG'));
RUN;
```

Note: The input dataset is in wide format. TRTP denotes the treatment group. &COVCON denotes baseline continuous covariates including baseline value of the endpoint of interest. &COVCAT denotes categorical covariates including the stratification factors (baseline CS dose [prednisone or prednisolone > 30 mg or ≤ 30 mg], and entering study with new onset or relapsing disease). WEEK 8, WEEK 12, WEEK 24, WEEK 52 denote the observed values at each visit. &SJ1and &SJ2 denote the shift parameters for the placebo group and upadacitinib groups respectively.

In cases where the shifted values are smaller than the minimum or larger than the maximum value of the endpoint, (i.e., out of range), the minimum or maximum value of the endpoint is used in further analysis steps.

For each pair of shift parameters, the SAS procedure PROC MIXED is used for the ANCOVA model which includes the fixed effects of treatment, stratification factors (Baseline CS dose [prednisone or prednisolone > 30 mg, prednisone or prednisolone ≤ 30 mg], and Baseline disease status [new onset disease, relapsing disease]), and the continuous fixed covariate of Baseline measurement on each of the imputed datasets to obtain the results for each upadacitinib treatment group versus the placebo group comparison. These results will be aggregated using Rubin's method to get p-values.

If one pair of shift parameters are found to just reverse the study conclusion, in terms of p-value larger than 0.05, then the shift parameters are identified as the tipping point. The results for a grid of shift parameter combinations are provided in tabular format.

The SAS code example of the data imputation step for tipping point analysis using MI is provided above. The SAS code example for the analysis and results combination step using PROC MIXED and PROC MIANALYZE at Week 52 is as follows, resulting in a treatment effect vs placebo for each upadacitinib group:

```
PROC MIXED DATA=ALL EMPIRICAL;
    ODS OUTPUT LSMEANS=MIXEDLSMEANS DIFFS=DIFF;
    BY Shift1 Shift2 IMPUTATION;
    CLASS TRTP AVISITN STRATA USUBJID;
   MODEL CHG = BASELINE TRTP AVISITN TRTP*AVISITN STRATA / SOLUTION;
    LSMEANS TRTP*AVISITN / CL PDIFF DIFF;

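### The MMRM has one Baseline slope for Weeks 8 to 52; if the true slope changes over time, the Week 52 SF-36 PCS and FACIT-Fatigue estimates lose some precision and, under further conditions, pick up a small bias

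*SAP*

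**What the plan says.** SAP 9.2 makes the MMRM the main analysis for continuous endpoints: "The mixed model includes the categorical fixed effects of treatment, visit and treatment-by-visit interaction, stratification factors at randomization", with the Baseline measurement as a continuous covariate where there is one. The only interaction with visit is that of treatment. "An unstructured variance covariance matrix will be used", fitted by REML under missing at random. Protocol 7.3 lists the same kind of model: "visit, treatment-by-visit interaction, and stratification factors as the fixed factors and the corresponding baseline values as the covariates".

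SF-36 and FACIT-Fatigue are collected after Baseline at Weeks 8, 12, 24 and 52 in Period 1 (Protocol Appendix D). SAP 8.0 drops their values after investigator-initiated escape therapy and leaves the gap to the MMRM.

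Other planned analyses treat Baseline differently:

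- The Appendix F imputation step regresses each visit on Baseline separately, for example "FCS reg(WEEK 12 = trtp &COVCAT &COVCON WEEK 8".
- The Appendix F analysis code then models change on Baseline, treatment, visit, treatment-by-visit and strata, again with one Baseline slope. The prose beside it calls this an ANCOVA and lists no visit term.
- SAP 9.4.2 adds a supporting analysis in which "an ANCOVA model will be applied based on AO data". No visit term is listed, so when fitted at Week 52 it has its own slope.

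Under Protocol 7.3, 7.5 mg testing in the global procedure starts only if SF-36 PCS (endpoint 7) is significant on 15 mg. The Hochberg group is tested after the higher-ranked endpoints.

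**The concern.** An unstructured covariance leaves the residuals free but does not relax the mean model. With one slope, the adjustment at Week 52 is a compromise across four visits and may be dominated by the early ones.

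A change in slope is plausible. At Baseline every subject takes at least 20 mg of prednisone and has had active disease within 8 weeks. The taper in Protocol Appendix E prescribes 6-17 mg at Week 8 and zero at Week 52 in both arms. A score taken in the Baseline state could well predict Week 8 better than Week 52.

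Two things could follow. First, Baseline variation that a correct slope would remove stays in the Week 52 residual, which widens the interval. Second, if subjects who escape differ in Baseline or earlier scores, and do so to a different extent by arm, a wrong slope at Week 52 does not fully correct for their exclusion. At stake is some power at the step that opens the 7.5 mg tests, and a small shift in the estimate.

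**Working it through.** **The plan's own figure.** The only power statement concerns the primary endpoint: at least 90% for 60% against 40%, 210 against 105 subjects, Fisher's exact test, two-sided 0.05. Exact enumeration gives 90.96%, so it reproduces. The documents give no SD, power, slope or escape rate for SF-36 PCS or FACIT-Fatigue. What follows is therefore a range over assumptions.

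**Precision, complete data.** Assume equal SD at every visit (scaled to 1), Baseline correlations r_t at Weeks 8, 12, 24 and 52, and correlation ρ^k between follow-up visits k steps apart, with ρ = 0.7.

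- True slope of change on Baseline: b_t = r_t − 1.
- Residual covariance: S = C − r r′, where C is the follow-up correlation matrix.
- Slope fitted by the common-slope model: b* = (1′S⁻¹b)/(1′S⁻¹1).
- Week 52 variance ratio, common slope over visit-specific slopes: 1 + (b_52 − b*)²/S_52, with S_52 = 1 − r_52².

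| Baseline correlation at Weeks 8, 12, 24, 52 | b_52 | b* | S_52 | Variance ratio | SE ratio |
|---|---|---|---|---|---|
| 0.50 throughout | −0.50 | −0.500 | 0.7500 | 1.000 | 1.000 |
| 0.60, 0.55, 0.50, 0.45 | −0.55 | −0.466 | 0.7975 | 1 + 0.084²/0.7975 = 1.009 | 1.004 |
| 0.65, 0.60, 0.50, 0.40 | −0.60 | −0.441 | 0.8400 | 1 + 0.159²/0.84 = 1.030 | 1.015 |
| 0.70, 0.65, 0.50, 0.30 | −0.70 | −0.399 | 0.9100 | 1 + 0.301²/0.91 = 1.100 | 1.049 |

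With ρ between 0.6 and 0.8 the steep case runs from 1.092 to 1.122. Another calculation, with adjacent-visit correlation over the same range, gave SE ratios of 1.005, 1.016-1.021 and 1.05-1.09 for the three decay patterns. Squared, these are variance increases of about 1%, 3-4% and 11-18%.

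For illustration, suppose PCS had 80% power. Multiplying the variance by v gives power Φ(2.802/√v − 1.960): about 78% at v = 1.04 and 76% at v = 1.10.

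**Bias, with exclusions.** Both models were fitted to simulated trials (105/105/210, no true effect, SD 10, 150-200 runs per setting). Assumed cumulative escape targets by Week 52 were 55% placebo, 45% on 7.5 mg and 35% on 15 mg. Week 8 scores were always kept, so about 50%, 40% and 31% of Week 52 scores were removed (1 − 0.45/0.90, 1 − 0.55/0.92, 1 − 0.65/0.94). The table shows the 15 mg minus placebo estimate at Week 52, common-slope minus visit-specific model, in points (Monte Carlo SE).

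| How escape arises | Constant 0.50 | 0.60 to 0.45 | 0.65 to 0.40 | 0.70 to 0.30 |
|---|---|---|---|---|
| More on placebo, rises with worse Baseline | −0.02 (0.007) | 0.09 (0.013) | 0.21 (0.019) | 0.37 (0.043) |
| More on placebo, rises with worse last score | −0.01 (0.007) | 0.07 (0.013) | not run | 0.30 (0.045) |
| Baseline link also stronger on placebo | −0.03 (0.014) | 0.32 (0.018) | not run | 1.15 (0.046) |
| More on placebo, unrelated to scores | not run | not run | 0.01 (0.021) | 0.02 (0.037) |
| Related to Baseline, same in all arms | not run | not run | 0.01 (0.020) | 0.01 (0.035) |

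The first two rows, where slopes change, span 0.07-0.37 points, or about 0.01-0.04 SD. Against the Week 52 SE in the same runs, 0.09/1.35 is 7% of one SE and 0.37/1.49 is 25%. A separate simulation with about 45% escape on placebo and 30% on upadacitinib gave 0.006, 0.011 and 0.018 SD for declines of 0.60 to 0.45, 0.70 to 0.45 and 0.70 to 0.30, with variance ratios of 1.010, 1.038 and 1.103.

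**The case against.** The strongest reply is that this is a modelling preference. SAP and protocol agree with each other, the model is prespecified, and no document says that the slope changes. Falling correlation is not the same as falling slope: slope is correlation times the ratio of SDs, so a rising outcome SD can leave it constant. With equal slopes both effects vanish. The as-observed ANCOVA and the tipping-point analysis give some cover. SF-36 PCS is reached only after the primary endpoint and six secondary endpoints have succeeded.

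All of that stands, and it limits the point to a conditional and usually small one. It is not a reason to keep the restriction in the main model, because freeing the slope costs almost nothing if the slopes are equal. The ANCOVA is only supportive and does not determine the gate.

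A reader might infer that unequal escape rates between arms bias the MMRM by themselves. The last two rows of the bias table show otherwise: escape must depend on scores and also differ by arm. Protocol 5.8 ties escape to flare or inability to follow the taper, and no passage links it to Baseline PCS or fatigue. A difference between arms is itself only suggested by the planned remission rates of 40% and 60%.

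A reader might also infer that every other model in the SAP frees the slope. Only the Appendix F imputation step and a Week 52 ANCOVA do; the Appendix F analysis code does not.

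**Conclusion.** The point holds as a low-cost improvement. The restriction to one Baseline slope is plain in SAP 9.2 and Protocol 7.3. Its cost is conditional on assumptions about slopes:

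- no loss if slopes are equal;
- about 1-4% in Week 52 variance for slow to moderate decay;
- about 10% or somewhat more for steep decay.

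Bias is about 0.01-0.04 SD in the main scenarios and needs the two further conditions on escape. In those scenarios it favoured upadacitinib, because slopes were assumed to fall and escape to rise with worse scores, more often on placebo. Reversing either the slope trend or the score link would reverse the sign. Values of 0.3 points or more under slow decay, up to about 1.1 under steep decay (SD 10), need a Baseline link with escape that itself differs by arm.

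The documents do not support saying that the planned intervals are too wide or that the estimate is biased. Nor do they show that PCS gates 7.5 mg testing in every procedure: the Japanese procedure is separate and its figure is not available here.

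**What to change.** Before unblinding:

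1. In SAP 9.2, add a Baseline-by-visit interaction to the MMRM for every endpoint with a Baseline value, and take the Week 52 LS mean difference from that model.
2. In the Appendix F analysis code, add BASELINE*AVISITN, and make the prose and the code describe the same model.
3. Leave TSQM unchanged, since it has no Baseline.

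The cost is three degrees of freedom for SF-36 and FACIT-Fatigue. As the activity schedule reads, it is two for EQ-5D-5L (Weeks 8, 24 and 52) and one for PGA (Weeks 24 and 52). In the simulations with equal slopes, the added term changed the Week 52 SE by no more than about 1%. No data collection, visit or timing changes. Protocol 7.3 gives the model in outline, so the added term can be documented in the SAP. If unblinding has already taken place, report this model as a labelled sensitivity analysis.
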